11.5.6 Safety Analyses

Descriptive statistics will be presented per study group for all safety parameters. The primary safety variable, the cumulative incidence (and 95% CI) of device related adverse events (AEs) throughout the study, will be presented in tabular format and will include incidence tables by severity.

Adverse event rates will be compared between the study groups with a Fisher's exact test.

Serious adverse events will be listed and discussed individually.

Treatment tolerability will be compared between the study groups. The number and percent of subjects who fail to complete the study and the number and percent of subjects who fail to complete the study because of Adverse Events will be presented as well.

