### **9.1.5. Visit 4 – end of the DB phase (Day 56±7)**

Written below are the assessments to be completed at Visit 4 (either on site or remotely):

[figure not shown]
- Depression symptoms questionnaires:
  - By site qualified rater: HDRS21 (HDRS17- removing 4 last questions from the HDRS21), MDRS, CGI-S & CGI-I
  - By subject: QIDS-SR-16, Q-LES-Q. Subject self-reported questionnaire may be filled in electronically (ePRO) or by hard copy.
- Suicidal intent assessment by the investigator team (C-SSRS)
- Change in concomitant medications, if any.
- Significant change in health status, if any.
- Adverse events will be documented.
  - The characteristics of each subject study treatments regimen will be indicated on the subject binder.
  - At the end of the double-blind treatment phase treatment compliance would be verified as follows:
    - A stimulation session marked as “Pass” if a minimal average intensity of 25 on the Relivion®DP app (i.e= Minimal average stimulation of 2.57mA Trigeminal, and 6.92mA Occipital of the active stimulation), was delivered.
    - The first treatment week (Ramp Up) will not be counted for treatment compliance.
    - Expected treatment time for total DB phase: A total of 2400 minutes of “pass” treatment time (calculated as a scenario of 80 min per day, 5 days a week for 6 weeks).
    - Minimal patient compliance for the DB treatment period will be regarded as 70% compliance to the above cumulative “pass” stimulation time recommendation.
- DB treatment regimen compliant subjects will be offered to continue to the open label extension phase for additional 8±1 weeks.
- Treatment regimen non-compliant subjects will exit the study and return the device and iPhone, if provided. For these subjects this study visit would be the “end of study visit”.

- Once the OL treatment regimen allocation will be decided, the central trainer will contact the subject (on site or remote) to perform the device conversion to the open label mode (i.e. conversion of all devices to active mode), train the subjects on the assigned treatment regimen and re-train on the device use, if required.
- OL treatment regimens would include:
  - Maintenance treatment (for remitters): 40±10 minutes 3-4 times a week (intensity level up to 50)
  - Daily treatment (for responders): 5-7 days a week (intensity level up to 50) 60±20 minutes per day (preferably in two equal sessions of 30±10 minutes each).

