  - Daily Intensified treatment regimen (for non-responders): 5-7 days a week (intensity level up to 60) 60±20 minutes per day (preferably in two equal sessions of 30±10 minutes each).
- Study visit 4 may occur during a 4 days period to allow for the HDRS response, treatment compliance assessments and OL treatment allocation to be finalized and data to be provided to the central trainer who may schedule a remote training session with the subject. In any case, the subject would continue his/her previous treatment regimen up until the day of the device conversion to the open label mode. The device conversion day would be considered as the first day of the OL treatment phase.
- Subjects which completed the minimal stimulation time required by the protocol will be considered as DB phase completers.

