### Figure 5: Open label phase study flow

- Subjects will operate the device along with the dedicated mobile application independently at home or surrounding, according to the recommended treatment regimen provided by the central trainer and on the “Relivion®DP quick guide” for 8±1 consecutive weeks. The Relivion®DP device programmed treatment duration will be 40 minutes. If needed, (i.e. for originally sham subjects who are not used to the active stimulation sensation) the daily treatment (duration and intensity) will be gradually increased up to a full effective treatment according to the assigned treatment regimen (i.e. for remitters, responders and non-responders). In general, it is expected that the responders and non-responders’ subjects recommended daily treatment time of 60±20 minutes would be performed in two equal time sessions per day (e.g. morning and evening, each of about 30±10 minutes). The remitters subjects would apply the stimulation once a day 3-4 times a week for 40+10 minutes. If necessary, treatment can be paused by the subject and then be resumed. Subjects will continue their assigned treatment regimen up to their scheduled visit 5 day. At study visit 5 the subjects response to treatment, according to HDRS, will be re-evaluated and treatment regimen may be amended accordingly (see Figure 5), re-training will be performed by central trainer, if required. The subjects will continue their assigned treatment regimen up to their scheduled visit 6 day (end of study).
- Subject will continue to self-complete the QIDS-SR-16 once every 7 days.
- The characteristics of each subject assigned study treatments regimen, both from visit 4 and visit 5 (if applicable), will be indicated on the subject binder.
- Study central trainer will periodically verify device logs on the study cloud database and may contact the subject for re-training, if required.
- Study team and central trainer will contact the subject periodically to troubleshoot any issue, If necessary.
- During this period, subject will be asked to schedule 2 follow-up evaluation visits (on-site or remote).

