2.2 Study Design

2.2.1 Experimental Design

This is a prospective, randomized, double-blind, parallel-group, sham controlled, multi-center clinical investigation followed by an active open label extension period. All enrolled patients are those treated with the Relivion®DP device either by active treatment or sham treatment. The treatment will be done according to the IFU. Patients' duration in the study will be up to 20 weeks (including the screening period).

In this study for the double-blind phase, the Relivion®DP was provided in therapeutic and non-therapeutic modes, for the Active and Sham groups respectively:

- Active Treatment: For the therapeutic mode the device will be preset to the following parameters: stimulation waveform- symmetrical biphasic, phase duration 130-300 microseconds, pulse frequency 80Hz, trigeminal stimulation intensity – up to 6.7mA, Occipital stimulation intensity– up to 18mA.
- Sham Control: For the non-therapeutic mode the device will be preset to the following parameters: Stimulation waveform- symmetrical biphasic, phase duration 100 microseconds, pulse frequency 0.33 Hz, trigeminal stimulation intensity up to 5mA, occipital stimulation

intensity up to 10mA for 3 minutes, then gradually decrease to 0.2 mA and stays constant throughout the remaining treatment duration.

Both Active and Sham stimulation devices are packaged and labeled identically to maintain blinding of both the subject and study staff.

The double blind Relivion®DP treatment will last 60±20 minutes (preferably in two equal sessions of 30±10 minutes each) per day for 5-7 days a week (intensity level up to 50) for a period of 8±1 weeks.

For purposes of the active open label phase, only active treatments were applied. Open label phase treatment regimens would be as follows, according to the subject HDRS score at the end of the double-blind phase, for a period of 8±1 weeks:

Maintenance treatment (for HDRS remitter subjects): 40±10 minutes 3-4 times a week (intensity level up to 50).

Daily treatment (for HDRS responder subjects): 5-7 days a week 60±20 minutes per day (preferably in two equal sessions of 30±10 minutes each).

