8.4 Safety Endpoints

Safety of the study device following study treatment: Incidence of adverse events and serious adverse events related or unrelated to the study device [Time Frame: up to 18 weeks post treatment initiation].

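### SAP 11.5.6 gives no period for the between-group adverse event comparison, so former sham subjects' events on active stimulation can count as sham; two subjects under 22 are in no safety set

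*SAP*

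**What the plan says.** SAP 11.5.6 has three relevant statements. "Descriptive statistics will be presented per study group for all safety parameters". The primary safety variable is "the cumulative incidence (and 95% CI) of device related adverse events (AEs) throughout the study". Then, as a separate statement: "Adverse event rates will be compared between the study groups with a Fisher's exact test". The last names no period. Protocol 12.9.4 uses the same wording.

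The nearest time window is in SAP 8.4: "up to 18 weeks post treatment initiation". The double-blind phase lasts 8±1 weeks, so this window runs into the open-label phase. Protocol section 11 collects AEs from randomization at Visit 2 to Visit 6.

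On open-label treatment, SAP 2.2.1 says: "For purposes of the active open label phase, only active treatments were applied". Protocol 9.1.5 describes "conversion of all devices to active mode" and fixes the date: "The device conversion day would be considered as the first day of the OL treatment phase". Only subjects who met the minimum stimulation requirement are offered the open-label phase, and they may decline (Protocol 8.2).

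On analysis sets, SAP 10.5 runs safety on ITT only. SAP 10.4 drops the separate mYITT analysis because only two subjects were under 22, and keeps those two out of the other sets. Protocol 12.7.5 had planned safety on both ITT and mYITT. SAP section 1 says the SAP prevails where the two differ.

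**The concern.** A between-arm AE comparison is meant to contrast active with sham stimulation. Once sham devices are converted, a table by randomized arm over the whole study contrasts active throughout with sham followed by active. The anticipated events in Protocol 11.2 are largely effects of stimulation, such as unpleasant sensation, numbness, tingling, pain and skin reactions. First exposure to active stimulation is therefore a plausible time for them, and for former sham subjects it falls in the open-label phase. Protocol 9.1.6 allows a gradual increase "for originally sham subjects who are not used to the active stimulation sensation". That is a ramp-up provision and says nothing of AEs, but it does recognise that active stimulation is new to these subjects.

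At stake is a table and p-value that can understate the device's AE excess in a pivotal study meant to support US and CE marketing applications. The two subjects under 22 are a smaller, separate matter: they were enrolled in an age range the protocol opened deliberately, yet their AEs would appear in no planned final safety table.

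**Working it through.** **Reading the text.** The steps are:

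1. The comparison is between study groups, with no period given (SAP 11.5.6).
2. The only periods nearby, the whole study and up to 18 weeks, both include open label (SAP 11.5.6 and 8.4).
3. Safety is run on ITT (SAP 10.5), and Protocol 12.7.1 groups ITT subjects as randomized. The SAP's own ITT definition was not in the text available to me, so grouping and age limits are taken from the protocol.
4. All open-label treatment is active (SAP 2.2.1).
5. No section limits the comparison to the double-blind phase or assigns AEs by treatment at onset. SAP 11.5.7, on the open-label stage, covers efficacy and satisfaction but not AEs.

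On the natural reading, post-conversion AEs of former sham subjects go in the sham column. The plan allows this without expressly requiring it.

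**Illustrating the effect.** The safety section states no figure to reproduce. Group sizes are 124/2 = 62 randomized per arm, or 53 evaluable per arm (Protocol 12.4). All risks and uptake below are assumptions.

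Let a and s be the double-blind risks of a device AE on active and sham. Let c be the share continuing, equal in both arms and independent of earlier AEs. Let r be the new-onset risk in continuing active subjects with no earlier device AE. Former sham subjects carry risk a on first active exposure.

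- Active, whole study: a + (1−a)·c·r
- Sham, whole study: s + (1−s)·c·a
- Difference: (a−s) + c·[(1−a)·r − (1−s)·a]

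Power is that of the exact two-sided Fisher test at 0.05, by enumerating both binomials. It counts rejection in either direction.

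At a = 30%, s = 10% and 62 per arm, the double-blind comparison has a 20-point difference and 74.9% power. In percentage points, the whole-study difference is 20 + c·(70r − 27):

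| c | r | Active % | Sham % | Difference (points) | Power % |
|---|---|---|---|---|---|
| 0.30 | 0 | 30.0 | 18.1 | +11.9 | 27.0 |
| 0.30 | 0.30 | 36.3 | 18.1 | +18.2 | 55.9 |
| 0.50 | 0 | 30.0 | 23.5 | +6.5 | 9.2 |
| 0.50 | 0.30 | 40.5 | 23.5 | +17.0 | 45.7 |
| 0.70 | 0 | 30.0 | 28.9 | +1.1 | 3.4 |
| 0.70 | 0.30 | 44.7 | 28.9 | +15.8 | 38.1 |
| 0.85 | 0 | 30.0 | 32.95 | −2.95 | 4.3 |
| 0.85 | 0.05 | 32.98 | 32.95 | 0.0 | 3.2 |
| 0.85 | 0.30 | 47.85 | 32.95 | +14.9 | 34.0 |
| 1.00 | 0 | 30.0 | 37.0 | −7.0 | 9.5 |
| 1.00 | 0.10 | 37.0 | 37.0 | 0.0 | 3.3 |
| 1.00 | 0.30 | 51.0 | 37.0 | +14.0 | 30.4 |

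The thresholds follow from the same formula:

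- The difference shrinks whenever r < 27/70 = 38.6%.
- With r = 0 it reverses only if c exceeds 20/27 = 74.1%.
- At c = 0.85 it reverses if r is below about 5%, and at c = 1 if r is below 10%.

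Other assumed cases, with c from 0.30 to 1 and r from 0 to a:

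- 30% v 10%, 53 per arm: power 67.7% falls to 3.0–47.9%.
- 25% v 5%, 62 per arm: 20 points becomes −3.7 to +18.5; power 86.0% falls to 3.1–64.7%.
- 20% v 10%, 62 per arm: 10 points becomes −8.0 to +9.4; power 25.9% falls to 2.9–19.0%.

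Unequal uptake matters. At 30% v 10% with r = 30%, 90% of active and 70% of sham continuing gives 48.9 v 28.9%, or +20.0 points and no net bias. The reverse uptake gives 44.7 v 34.3%, or +10.4 points.

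**Subjects under 22.** SAP 10.4 removes them from the other sets, and SAP 10.5 runs safety on ITT alone. They are in no planned incidence table or Fisher test. If 124 older subjects were enrolled, this is 2/126 = 1.6%.

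**The case against.** The strongest reply is that the whole-study wording belongs to a descriptive presentation, while the Fisher sentence stands apart and speaks of study groups. When the SAP handles open-label data it uses other terms, such as the original active group or all subjects regardless of prior treatment. So the comparison could be meant as double-blind only. That reading is possible, but nothing in the text secures it, and the periods stated nearby point the other way.

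On size, Protocol 7.6.2 reports similar AE incidence in both groups of the pivotal migraine trial of the similar device, and a single mild AE in the first-in-human study. Exposure there was different, but a small excess here is possible. At 5% v 3% with r = 5%, the model moves 2.0 points only to 1.9–2.0, and Fisher power is 1–4% throughout. With r = 0 the difference is 2.0 − 4.85c, that is +0.5 at c = 0.30 and −2.85 at c = 1. Nor can r above a be excluded, since double-blind non-responders move to a higher intensity ceiling. At 30% v 10% and an extreme r of 60%, the difference is 20 + 15c, or 24.5 to 35 points. These points stand: neither the size nor the direction of the bias is certain. They do not make the mixed comparison a valid one of active with sham.

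On consequence, no success rule or safety hypothesis depends on the test. Serious AEs are listed individually, and Protocol 11.3.7 requires narratives and adjudication for device-related events and sends all safety data to the data monitoring committee. Events in the two younger subjects would be collected and, if device-related, adjudicated. All this limits the harm to misleading or incomplete tables. The SAP also gives its reason for dropping mYITT. Small numbers justify dropping a separate efficacy analysis, but not leaving exposed subjects out of the safety tables.

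**Conclusion.** The concern holds on both parts and should be fixed. The plan permits, and most naturally implies, a by-arm AE comparison in which active exposure enters the sham column. With equal uptake, this shrinks the difference if active causes more device AEs than sham and the new-onset risk in continuing active subjects is no higher than the first-exposure risk. The actual size cannot be derived from the documents. Under the assumed rates it ranges from slight to a reversal of sign, and unequal uptake or a high later risk can cancel it or widen the difference. The finding rests on the text, not on those figures.

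The omission of two subjects follows directly from SAP 10.4 and 10.5. SAP 2.2.1 says safety was assessed in mYITT at the interim, but whether these two were enrolled by then is not stated.

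**What to change.** - In SAP 11.5.6, base the between-arm AE comparison and Fisher test on AEs with onset from randomization, including device practice at Visit 2, to device conversion or study exit.
- Keep the pre-specified whole-study incidence as a descriptive table, noting that the sham column includes active exposure after conversion.
- Add a separate table of open-label AEs, by original arm and pooled over active exposure.
- In SAP 10.5, run safety on all subjects of any age exposed to a study device, including Visit 2 practice. This brings in the two subjects under 22.

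The cost is SAP wording and one onset-phase flag, built from the AE start date (Protocol 11.3.1) and the device conversion day (Protocol 9.1.5), plus two more subjects in the safety tables. No new data are needed and no success rule changes.

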### **5.1.3. Safety Objective**

To demonstrate safety in using the Relivion®DP device in subjects suffering from Major Depressive Disorder (MDD).

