We use conservative estimates of a 3.3-point difference with a standard deviation of 6 points. Calculations show that a sample size of 53 subjects per group (total 106) would provide 80% power at a 5% level of significance (two-sided) to detect the difference between treatment and sham groups.

Given our preliminary results, together with other companies clinically relevant data, we hypothesize that our statistical assumptions are aligned with competitive treatments for MDD.

The company anticipates that after randomization, but before the endpoint can be observed, up to 15% of the subjects will drop out from the study irrespective of study arm and success of treatment; thus, an adjustment for this drop-out rate is made and a sample size of 124 is required at the point of randomization.

We shall randomize an additional up to 36 subjects (30+15% dropout) in the age range 18-21 to assess efficacy in this age range as well.

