2. STUDY DESIGN AND OBJECTIVE

2.1 Study Objectives

The main objective of the study is to evaluate the safety and efficacy of a self-administered treatment for MDD using an external combined occipital and trigeminal nerve stimulator (Relivion®DP). This pivotal clinical investigation is intended to support future marketing applications (US FDA and CE) for Neurolief's Relivion®DP device.

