9. SIGNIFICANCE LEVELS AND HANDLING OF TYPE I ERROR

9.1 Type I error

The overall significance level for this study is 5% using two-tailed tests, except for treatment by site interaction that will be tested at a significance level of 10% and the test for early efficacy at the interim look.

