11.5.3 Pooling

Subgroup analysis of the primary efficacy endpoint by comparing clinical centers will be used to evaluate the poolability of the results. Treatment by center interaction will be tested in the primary analysis model at a significance level of 10%. This interaction term is not part of the primary endpoint model. If the interaction is found significant the reason for this interaction will be further explored and rationalized. This evaluation may include demographic features, symptoms at presentation, and clinical and treatment history, and center comparability in the features found to be associated with the primary efficacy variable.

In the case that poolability is questionable, the reasons for differential treatment effect, such as subject and clinical characteristics, will be investigated and reported.

11.5.4 Secondary Efficacy Endpoint Analyses:

- Proportion of responder subjects- defined as the percent of subjects achieving at least 50% reduction from baseline in their HDRS-17 total score, 8 weeks post Relivion®DP treatment initiation - will be summarized by a count and percentage and compared between the groups with a chi-squared test and a Fisher's exact test. The odds ratio with 95% Wald confidence interval will be presented as well. As an additional measure of effect size the NNT will be presented. If covariates are identified in the prognostic factor analysis, logistic regression will be performed as well adjusting for the identified factors.
- Proportion of subjects achieving remission- defined as the percent of subjects with HDRS-17 score≤7 at 8 weeks post Relivion®DP treatment initiation- will be summarized by a count and percentage and compared between the groups with a chi-squared test and a Fisher's exact test. The odds ratio with 95% Wald confidence interval will be presented as well. As an additional measure of effect size the NNT will be presented. If covariates are identified in the prognostic factor analysis logistic regression will be performed as well adjusting for the identified factors.

- Mean change in depressive symptoms, measured by MADRS total score, from baseline to week-8 post treatment initiation - will be compared between the groups using a similar model as the primary endpoint.

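### Adverse event rates are compared between arms by Fisher's exact test alone, with no risk difference or between-arm interval and no restriction to the double-blind phase

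*SAP*

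**What the plan says.** Protocol 5.1.3 opens the safety objective with "To demonstrate safety in using the" device in subjects with MDD. SAP 2.1 is softer: "The main objective of the study is to evaluate the safety and efficacy of a self-administered treatment for MDD". SAP section 1 says that the SAP prevails where the two differ. Neither document sets a safety hypothesis, a margin or an acceptable rate.

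On analysis, SAP 11.5.6 plans descriptive statistics per group and then: "The primary safety variable, the cumulative incidence (and 95% CI) of device related adverse events (AEs) throughout the study, will be presented in tabular format". Severity tables follow. For the contrast between arms it says: "Adverse event rates will be compared between the study groups with a Fisher's exact test". SAEs are listed and discussed one by one. Tolerability is to be compared without a named method, and non-completers, overall and because of AEs, are counted. Protocol 12.9.4 carries the same AE comparison.

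For binary efficacy endpoints the SAP goes further. In 11.5.4, for response and again for remission, it adds: "The odds ratio with 95% Wald confidence interval will be presented as well", together with an NNT. SAP 11.5.5 does the same for the 7-point HDRS-17 reduction.

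On timing, the safety endpoint runs up to 18 weeks after treatment start (protocol 5.1.7, SAP 8.4), and the primary safety variable covers the whole study. Protocol 6.3.2 and 9.1.5 have sham devices converted to active after visit 4, at about week 8.

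**The concern.** A Fisher p-value says whether equality of two rates is contradicted by the data. It says nothing about how large an excess on active stimulation remains compatible with them. The sample size was set on HDRS-17 alone, so nothing ensures that a non-significant AE comparison is informative.

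This is a pivotal trial meant to support marketing applications. As planned, a reader will see the size and uncertainty of the benefit on each binary endpoint, but for harm only two incidences and a p-value. If that p-value is above 0.05, it could easily be summarised as no difference in AEs when a clinically relevant excess has not been excluded. Counting open-label events in both arms would pull the two rates together and make that outcome more likely.

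**Working it through.** **Inputs from the documents.** Two-sided 5% level: "The overall significance level for this study is 5% using two-tailed tests" (SAP 9.1). Planning assumptions: "We use conservative estimates of a 3.3-point difference with a standard deviation of 6 points" (protocol 12.4). Evaluable size is 53 per group and randomized size is 124 after 15% dropout (protocol 12.4). The 124 was kept after the interim analysis (SAP 2.2.1). Allocation is 1:1 (SAP 6). Safety is analysed on the ITT set (SAP 10.5), so at most 62 per arm.

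**Assumed input.** The sham AE rate. The documents give none for this trial. The only AE count is one mild event among 30 treated subjects in an early migraine study of an earlier device iteration (protocol 7.6.2), which is weak guidance. The range used below is 5% to 30%.

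**The plan's own figure.** For a 3.3-point difference and SD 6, the two-sample t-test with 53 per group has 80.1% power, which reproduces the planned figure. 106/0.85 = 124.7, against 124 stated. No such calculation exists for safety.

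**Power of the planned AE test.** With n per arm, sham rate p and active rate 2p, power is the sum, over all pairs (i, j), of Bin(i; n, 2p) × Bin(j; n, p), counting only pairs whose two-sided Fisher p-value is 0.05 or less. This is exact enumeration.

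| Sham to active | 53 per arm | 62 per arm |
|---|---|---|
| 5% to 10% | 7% | 9% |
| 10% to 20% | 21% | 26% |
| 15% to 30% | 38% | 44% |
| 20% to 40% | 54% | 62% |
| 25% to 50% | 71% | 78% |
| 30% to 60% | 84% | 91% |

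Power passes 50% at a sham rate of about 19% (53 per arm) or 17% (62 per arm), and 80% at about 28.5% or 26%. By the pooled two-proportion formula without continuity correction, 80% power for a doubling needs 435 per arm at 5% to 10%, 199 at 10% to 20% and 121 at 15% to 30%.

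**What an interval would add.** Take 12 against 6 subjects with an AE among 62 per arm. Fisher's p = 0.20. The rates are 0.1935 and 0.0968, a difference of 0.0968. Their Wilson 95% limits are (0.1143, 0.3085) and (0.0451, 0.1955). Newcombe's interval for the difference is then:

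- lower: 0.0968 − √[(0.1935 − 0.1143)² + (0.1955 − 0.0968)²] = −0.030
- upper: 0.0968 + √[(0.3085 − 0.1935)² + (0.0968 − 0.0451)²] = +0.223

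The p-value alone looks reassuring, but the interval does not exclude an excess of 22 points. Likewise, 9 against 3 gives p = 0.13 and +9.7 points (95% CI −1.1 to +21.0), and 6 against 3 gives p = 0.49 and +4.8 points (95% CI −5.1 to +15.2).

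**Effect of the open-label phase.** As an illustration, suppose 8-week AE risks of 10% on sham and 20% on active, everyone enters the open-label phase, all then face a 20% risk, and the phases are independent. Cumulative risk is 1 − 0.90 × 0.80 = 28% in the original sham arm and 1 − 0.80 × 0.80 = 36% in the original active arm. The ratio falls from 2.0 to 36/28 = 1.29 and the difference from 10 to 8 points. By the same enumeration, Fisher power falls from 26% to 12% at 62 per arm, and from 21% to 10% at 53.

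**The case against.** The strongest reply is that no comparative safety claim is planned. The safety objective does not mention sham, whereas the efficacy objectives do. The SAP says only that safety is evaluated, and formal hypotheses exist only for HDRS-17. On that view, incidence with a 95% CI is the matching analysis and the Fisher test is supplementary. This explains the absence of a margin, and none needs to be added. It does not explain why, having chosen to compare arms, the plan gives a test without an estimate.

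A reader might infer that the Fisher p-value is the only safety output. The documents do not support that. SAP 11.5.6 also plans per-group descriptives, an incidence interval, severity tables, SAE listings and a tolerability comparison. SAP 11.3 adds disposition and time to withdrawal by group, and a DMC reviews safety (protocol 14.1). The per-group counts would let a reader compute a risk difference, but the plan does not commit to reporting one.

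A reader might also infer that the plan will take p > 0.05 as proof of safety. Neither document says so. The risk lies in interpretation, and one sentence in the SAP would remove it.

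Finally, a reader might infer that the trial misses a doubling of AEs most of the time whatever the rate. That is not supported either: at 30% against 60% power is 91% with 62 per arm, so for a common outcome the test may be adequate. The documents set no power target for safety.

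**Conclusion.** The point holds as a gap in the comparative AE analysis. Fisher's test is the only named between-arm method for AE rates, it comes without a risk difference or interval, and it is not confined to the randomized, blinded comparison. For sham rates below about 17% (62 per arm) or 19% (53 per arm), it has less than even odds of detecting a doubling, so a non-significant result cannot bound excess harm. These thresholds rest on assumed AE rates, independent binomial counts and a clean active-sham contrast. Open-label events would weaken that contrast. The conclusion that a p-value does not bound harm does not depend on the rates. The finding concerns analysis and reporting, and does not show that the trial is too small or that its other safety outputs are deficient.

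**What to change.** In SAP 11.5.6, with protocol 12.9.4 aligned:

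1. For the double-blind phase, report the active-minus-sham risk difference with a 95% CI (for example Miettinen-Nurminen) for any AE, device-related AEs and SAEs, beside the Fisher p-value.
2. Restrict the between-arm comparison to events before device conversion at visit 4, and tabulate open-label events separately by original arm.
3. State that any comparative safety statement rests on the interval, including its upper limit, and that a non-significant Fisher test will not be read as evidence of equal safety.

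This needs no new data: some SAP wording, one extra column in the AE tables and a split of those tables by phase. The downside is that the intervals will be wide, as the illustrations show, so safety statements will have to be more cautious.
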